2. INTRODUCTION

2.1. Study Rationale

The aim of this Phase 2 study is to identify common or unique adaptive and innate immune signals or inflammatory biomarkers with predictive value for mRNA vaccine-induced immunogenicity and/or reactogenicity to support the Sponsor's mRNA-based vaccine platform and mRNA-1010 vaccine development. CCI [REDACTED]

[REDACTED]

2.2. Background

ModernaTX, Inc. (the Sponsor) has developed a proprietary vaccine platform based on mRNA delivered through LNPs. The platform is based on the principle and observations that cells in vivo can take up LNP-encapsulated mRNA, translate it, and then express protein antigen(s) on the cell surface or secrete the antigens. The intracellularly delivered mRNA does not enter the cellular nucleus or interact with the genome, is nonreplicating, and is expressed transiently. Strongly encouraged by the successful development of its mRNA-based SARS-CoV-2 vaccine (mRNA-1273; Spikevax®), the Sponsor is currently using the mRNA/LNP-based vaccine delivery platform to develop vaccines against multiple viruses, including influenza (mRNA-1010), RSV (mRNA-1345), and cytomegalovirus (mRNA-1647).

mRNA-1010 is an LNP-encapsulated, mRNA-based, prophylactic vaccine containing 4 mRNAs in an equivalent mRNA mass ratio that encode membrane-bound HA of the 4 different influenza strains, recommended by the WHO for 2022-2023 NH cell or recombinant based vaccines. The Sponsor has completed a Phase 1/2 study of mRNA-1010 (NCT04956575) at dose levels up to CCI and is now conducting several Phase 3 studies at a CCI dose level (NCT05415462 and NCT05566639).

This study will evaluate several versions of the Sponsor's seasonal influenza mRNA vaccine candidate (mRNA-1010) that are currently being evaluated in separate clinical Phase 1/2 (mRNA-1083-P101) and Phase 3 development studies (mRNA-1010-P303) for their ability to further optimize the immunogenicity and tolerability of the mRNA-1010 vaccine. CCI

[REDACTED]

Additional details of mRNA-1010 are provided in the IB.

2.3. Benefit/Risk Assessment

2.3.1. Risk Assessment

There have been very rare (<1 in 10,000 recipients) reports of myocarditis and pericarditis occurring after vaccination with COVID-19 vaccines, including mRNA vaccines. The majority

of the cases have been reported in adolescents and young males shortly after the second or subsequent doses of the vaccine. These are typically mild cases, and individuals tend to recover within a short time following conservative treatment (including rest, NSAIDs, and/or colchicine). Healthcare professionals and study participants should be alert to the signs and symptoms of myocarditis and pericarditis ([Gargano et al 2021](#)). It is not known whether the risk of myocarditis or pericarditis is increased following additional doses of other non-COVID mRNA vaccines.

Safety and reactogenicity data from multiple studies with mRNA-1010 (NCT04956575, NCT05415462, and NCT05566639) have revealed no safety concerns to date. Additional details are provided in the IB.

2.3.2. Benefit Assessment

Participants will obtain information about their general health status through the medical evaluations/assessments associated with this study (eg, physical examination, vital signs measurement, and symptom-directed physical examination).

Participants will be contributing to the process of developing a new potentially prophylactic measure for infection with influenza or other pathogens.

2.3.3. Overall Benefit/Risk Conclusion

Considering the safety data for mRNA-1010 to date, the Sponsor considers the potential benefits of participation to exceed the risks.

3. OBJECTIVES AND ENDPOINTS

Table 2: Objectives and Endpoints

Objectives	Endpoints
Primary	

 To evaluate the safety and reactogenicity of mRNA-1010 vaccine candidate variations. 	
 Solicited local and systemic ARs through 7 days after study intervention. Unsolicited AEs through 28 days after study intervention. Medically attended AEs from Day 1 to EoS. AESIs from Day 1 to EoS. SAEs from Day 1 to EoS. AEs leading to study or treatment discontinuation from Day 1 to EoS.
Secondary	

 To evaluate the humoral immunogenicity of mRNA-1010 vaccine candidate variations at evaluable humoral immunogenicity timepoints. 	
 GMT at indicated timepoints as measured by HAI assay. GMFR, comparing each timepoint with D1 (Baseline) as measured by HAI assay. Percentage of participants with seroresponse^a for mRNA-1010 at indicated timepoints, as measured by HAI assay.

CCI

Abbreviations: AE=adverse event; AESI=adverse events of special interest; AR=adverse reaction; D=day; EoS=end-of-study; GMFR=geometric mean fold rise; GMT=geometric mean titer; HAI=hemagglutination inhibition; LLOQ=lower limit of quantification; SAE=serious adverse event.

^a Vaccine seroresponse is defined as an increase of antibody titers and concentrations from predose below the LLOQ to $\geq 4 \times$ LLOQ, or at least a 4-fold rise if predose is \geq LLOQ.

4. STUDY DESIGN

4.1. Overall Design

This will be a randomized, observer-blind, Phase 2 study to evaluate the safety, reactogenicity and immunogenicity of mRNA-1010 vaccine candidate variations using a systems biology approach in healthy adults 18 to 49 years of age.

Three mRNA-1010 vaccine candidate versions will be evaluated ([Table 3](#)):

- mRNA-1010: CCI [REDACTED]
- mRNA-1010.4: CCI [REDACTED]
- mRNA-1010.6: CCI [REDACTED]

CCI [REDACTED]

This study will initially enroll approximately 270 participants 18 to 49 years of age. Participants will be randomly assigned to study arms 1, 2, 3, 4, 5, and 6 in a ratio of 2:1:2:1:1:2 to receive a single dose of 1 of the 3 mRNA-1010 vaccine candidate variations (ie, mRNA-1010, mRNA-1010.4, or mRNA-1010.6). Randomization will be stratified by receipt of a 2022-2023 NH influenza vaccine (Yes/No). The different arms will include different dose levels for mRNA-1010.4 and mRNA-1010.6. See [Table 4](#) for study arms and number of participants per study arm.

Except for appropriately delegated unblinded pharmacists, vaccine administrators, and monitors, all personnel involved in the conduct of the study will remain blinded to individual treatment assignment until planned study unblinding.

Study visits for all participants will consist of a Screening Visit (up to 28 days before the D1 visit), a Study Intervention Visit at D1, and Clinic Visits CCI [REDACTED]

[REDACTED] The duration of study participation for all participants is up to 7 months from the Screening Visit. Refer to the SoA ([Table 1](#)), for more details.

Safety Oversight

Safety monitoring for this study will include the blinded study team members, including, at least, the Sponsor Medical Monitor, a CRO Medical Monitor, a Clinical Safety Physician, and an unblinded IST. The unblinded IST will comprise 3 members who are not directly involved in the conduct of this study. The study team will conduct ongoing blinded safety reviews during the study and will be responsible for notifying the unblinded IST in case of potential safety signal events. Details regarding composition, responsibilities, and procedures of the IST will be presented in the IST charter.

An independent CEAC of medically qualified personnel, including cardiologists, will review all suspected cases of myocarditis and pericarditis to determine if they meet CDC criteria of “probable” or “confirmed” events which are reported in ongoing interventional clinical trials per the CEAC charter ([Gargano et al 2021](#)).

4.2. Scientific Rationale for Study Design

The study is designed as a randomized, observer-blind dose-ranging study to evaluate the safety, reactogenicity, and immunogenicity of mRNA vaccine candidate variations in healthy adults 18 to 49 years of age. The randomized and observer-blind design will ensure unbiased collection of safety and immunogenicity data.

This study will evaluate several versions of the Sponsor’s seasonal influenza mRNA vaccine candidate (mRNA-1010). CCI [REDACTED]

This study will be performed in an exploratory manner CCI [REDACTED]

4.3. Justification for Dose

Participants will receive either 1 dose level of mRNA-1010 CCI [REDACTED] 1 of 2 dose levels of mRNA-1010.4 CCI [REDACTED]); or 1 of 3 dose levels of mRNA-1010.6 CCI [REDACTED] administered on Day 1 (refer to [Table 3](#)).

The selected dose levels in this study are based on the observed reactogenicity and immunogenicity profiles in clinical Phase 1/2 and Phase 3 studies conducted with mRNA-1010

At least 15,000 adults have been dosed with mRNA-1010. No safety concerns were identified with mRNA-1010 dose levels up to CCI [REDACTED]

4.4. End-of-Study Definition

The EoS is defined as the date of the last visit of the last participant in the study or last scheduled procedure as shown in the SoA ([Table 1](#)) for the last participant in the study.

A participant is considered to have completed the study if he or she has completed all parts of the study, including the last visit or scheduled procedure as shown in the SoA ([Table 1](#)).

5. STUDY POPULATION

Prospective approval of protocol deviations to recruitment and enrollment criteria, also known as protocol waivers or exemptions, is not permitted.

5.1. Inclusion Criteria

Participants are eligible to be included in the study only if all of the following criteria apply:

Age

1. Adults 18 to 49 years of age at the time of consent (Screening Visit) who, in the opinion of the Investigator, are in good health based on review of medical history and physical examination performed at screening.

Sex and Contraceptive/Barrier Requirements

2. A participant AFAB is eligible to participate if not pregnant or breastfeeding, and one of the following conditions applies:

- Is a PONCBP as defined in Clinical Study Protocol, [Appendix 4](#).

OR

- Is a POCBP and using an acceptable contraceptive method as described in [Appendix 4](#) at least 28 days before the dose of study intervention and for at least 3 months after the dose of study intervention. The Investigator should evaluate the potential for contraceptive method failure (eg, noncompliance, recently initiated) in relationship to the dose of study intervention.

A POCBP must have a negative highly sensitive pregnancy test (urine or serum as required by local regulations) at the Screening Visit and again before the dose of study intervention if Day 1 is not on the same day as the Screening Visit (see [Section 8.3.3](#)).

- If a urine test cannot be confirmed as negative (eg, an ambiguous result), a serum pregnancy test is required. If the serum pregnancy result is positive, the participant must be excluded from participation.

The Investigator is responsible for review of medical history, menstrual history, and recent sexual activity to decrease the risk for inclusion of a participant with an early undetected pregnancy.

Informed Consent

3. Capable of giving signed informed consent as described in [Section 10.1.3](#), which includes compliance with the requirements and restrictions listed in the ICF and in this protocol.
4. Participant has provided written informed consent for participation in this study, including all evaluations and procedures as specified in this protocol.

5.2. Exclusion Criteria

Participants are excluded from the study if any of the following criteria apply:

Medical Conditions

5. Participant has had close contact with someone with laboratory-confirmed influenza infection or with someone who has been treated with antiviral therapies for influenza (eg, Tamiflu®) within the past 5 days prior to D1.
6. Participant has tested positive for influenza by local health authority-approved testing methods within 150 days prior to D1.
7. Is acutely ill or febrile (temperature $\geq 38.0^{\circ}\text{C}/100.4^{\circ}\text{F}$) within 72 hours prior to or at the Screening Visit or D1. Participants meeting this criterion may be rescheduled within the 28-day Screening window and will retain their initially assigned participant number.
8. History of a diagnosis or condition that, in the judgment of the Investigator, is clinically unstable or may affect participant safety, assessment of safety endpoints, assessment of immune response, or adherence to study procedures. Clinically unstable is defined as a diagnosis or condition requiring significant changes in management or medication within the 60 days prior to Screening and includes ongoing workup of an undiagnosed illness that could lead to a new diagnosis or condition.
9. Asymptomatic conditions and conditions with no evidence of end-organ involvement (eg, mild hypertension, dyslipidemia) are not exclusionary, provided that they are being appropriately managed and are clinically stable (ie, unlikely to result in symptomatic illness within the time-course of this study). Illnesses or conditions may be exclusionary, even if otherwise stable, because of immunosuppressive therapies (drugs or biologics) used to treat them, at the discretion of the Investigator.
 - Participants who have undergone surgical procedures within 7 days prior to Day 1 or are scheduled to undergo a surgical procedure within 28 days after study injection are also excluded. However, minor surgical procedures under local anesthesia (eg, excision of skin lesion) or diagnostic procedures (eg, colonoscopy) are allowed.
10. Any medical, psychiatric, or occupational condition, including reported history of substance abuse, that may pose additional risk as a result of participation, or that could interfere with safety assessments or interpretation of results according to the Investigator's judgment.
11. Has a current or previous diagnosis of congenital or acquired immunodeficiency, to include HIV, immunosuppressive condition or immune-mediated (autoimmune) disease, asplenia, or recurrent severe infections, that requires treatment with systemic immunosuppressive drugs or biologics. Participants who use topical corticosteroids or other immunosuppressive agents (eg, topical calcineurin inhibitor) may be eligible for participation at the discretion of the Investigator.
12. History of anaphylaxis, urticaria, or other significant AR requiring medical intervention after receipt of mRNA vaccines or any components of the mRNA-1010 or influenza vaccines, including egg protein.

13. Any history of myocarditis or pericarditis.
14. Reported history of coagulopathy or bleeding disorder considered a contraindication to IM injection or phlebotomy.
15. Dermatologic conditions that could affect local solicited AR assessments (eg, tattoos, psoriasis patches affecting skin over the deltoid areas).
16. Diagnosis of malignancy within the previous 2 years (excluding nonmelanoma skin cancer).
17. History of Guillain-Barre syndrome.

Prior/Concomitant Therapy

18. Has received systemic immunosuppressive therapy (drugs or biologics) for more than 14 days within 180 days prior to Screening (for corticosteroids ≥ 10 mg/day of prednisone equivalent) or is anticipating the need for systemic immunosuppressive treatment at any time during participation in the study. Inhaled, nasal, and topical steroids are allowed. Intra-articular and epidural steroid injections are not allowed within 28 days before and/or after study intervention dosing.
19. Has received or plans to receive any licensed/authorized vaccine (to include SARS-CoV-2 vaccine) ≤ 28 days prior to or within 28 days after study intervention.
20. Has received a licensed seasonal influenza vaccine within 5 months (150 days) prior to D1.
21. Has participated in any investigational seasonal influenza vaccine study within 12 months prior to D1.
22. Is not aware of having received a seasonal influenza vaccine in the most recent influenza season (in the prior 12 months).
23. Has been treated with antiviral therapies for influenza (eg, Tamiflu®) within 150 days prior to D1.
24. Has received systemic immunoglobulins or blood products within 90 days prior to the Screening Visit or plans to receive the treatment during the study. In addition, participants who have received long-acting biological therapies that affect immune responses (eg, infliximab) within 90 days prior to the Screening Visit/Day 1, or plan to receive them, are also excluded.

Prior/Concurrent Clinical Study Experience

25. Has donated ≥ 450 mL of blood products within 28 days prior to the Screening Visit or plans to donate blood products during the study.
26. Participated in an interventional clinical study within 28 days prior to the Screening Visit based on the medical history interview or plans to participate in an interventional clinical trial of an investigational vaccine or drug while participating in this study.

Other Exclusion Criteria

27. Is working or has worked as study personnel or is an immediate family member or household member of study personnel, study site staff, or Sponsor personnel.

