- a. Participants may experience AEs that necessitate a USV. Additional examinations may be conducted at these visits as necessary to ensure the safety and well-being of participants during the study.
- b. The Screening Visit and Day 1 may be performed on the same day or a different day. Additionally, the Screening Visit may be performed over multiple visits if within the 28-day screening window. If a participant returns for the D1 visit more than 28 days after their Screening Visit for any reason and continues to provide consent to participate in the study, the participant may be rescreened, for study eligibility. All assessments for eligibility must be repeated.
- c. A blood draw will be collected at 6 hours post vaccine injection on D1.
- d. A full physical examination, including height, weight, and BMI will be performed at Screening. Symptom-directed physical examinations may be performed at other timepoints at discretion of the Investigator. On each dosing day before injection, the arm receiving the injection should be examined and the associated lymph nodes should be evaluated. Any clinically significant finding identified by a healthcare professional during study visits should be reported as an MAAE.
- e. Vital signs measurements: Systolic and diastolic blood pressures, pulse rate, respiratory rate, and body temperature. The preferred route of temperature assessment is oral. On the day of vaccination, vital signs will be collected once before vaccination and once at least 30 minutes after vaccination. Vital signs may be collected at other clinic visits in conjunction with a symptom-directed physical examination.
- f. A pregnancy test either via blood or point-of-care urine test will be performed at the Screening Visit and before the vaccine dose on Day 1, if Day 1 is not on the same day as the Screening Visit. At the discretion of the Investigator, a pregnancy test either via blood or point-of-care urine can be performed at any time. If a urine test cannot be confirmed as negative (eg, an ambiguous result), a serum pregnancy test is required. The participant’s FSH level may be measured at the Screening Visit, as necessary, and at the discretion of the Investigator, to confirm postmenopausal status.
- g. D1 (Baseline) blood samples for **CCI** [REDACTED]

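### The main look-backs of exclusion criteria 24 and 25, and to a lesser extent 18 and 26, stop at Screening, so an unplanned exposure between Screening and Day 1 meets no mandatory exclusion

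*Protocol*

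**What the plan says.** Protocol Section 4.1 allows Screening up to 28 days before Day 1, and footnote b of the Schedule of Activities (Section 1.3) adds: "The Screening Visit and Day 1 may be performed on the same day or a different day". The schedule marks the eligibility criteria for review at both Screening and Visit 1.

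In Section 5.2, four criteria have a main look-back that ends at Screening:

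- Criterion 18, systemic immunosuppressants: "for more than 14 days within 180 days prior to Screening". Its forward clause applies if the participant "is anticipating the need for systemic immunosuppressive treatment at any time during participation in the study".
- Criterion 24, first sentence: "Has received systemic immunoglobulins or blood products within 90 days prior to the Screening Visit or plans to receive the treatment during the study".
- Criterion 25, donation of at least 450 mL: "within 28 days prior to the Screening Visit or plans to donate blood products during the study".
- Criterion 26, other interventional studies: 28 days before Screening, or plans to join one while taking part in this study.

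Other clauses use a later anchor:

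- Criterion 24, second sentence (long-acting biologics): "within 90 days prior to the Screening Visit/Day 1, or plan to receive them, are also excluded".
- Criterion 18, last sentence: "Intra-articular and epidural steroid injections are not allowed within 28 days before and/or after study intervention dosing".
- Criteria 5, 6, 20, 21 and 23 count back from Day 1, and criterion 19 from the study intervention.

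**The concern.** A look-back that ends at Screening, joined to a clause about intentions, leaves a span that neither part covers. Suppose a participant receives a blood product or gives a large donation after Screening without having planned it, and the event is over by Day 1. The event is not before Screening, and on Day 1 it is no longer a plan. The second eligibility review does not help, because it applies the same words.

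Two things are at stake. Immunosuppressants, immunoglobulins and blood products are exposures that Section 6.9.2 itself treats as relevant to per-protocol evaluability, so they bear on the HAI endpoints. A recent large donation bears on blood sampling: the synopsis describes frequent samples over the first 7 days, and the schedule includes one at 6 hours after injection.

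The protocol gives no reason for using different anchors, and criterion 24 changes anchor from one sentence to the next.

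**Working it through.** The plan states no figure on this point, so there is none to reproduce. The check is interval arithmetic on the stated windows, followed by an illustrative count.

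**Step 1: what each look-back covers.** Let g be the days from Screening to Day 1 (0 to 28) and L the look-back length. Counted backwards from dosing, a look-back that ends at Screening covers days g to g + L. At g = 28:

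| Criterion | L (days) | Days before dosing covered | Not covered |
|---|---|---|---|
| 18, main clause | 180 | 28 to 208 | 0 to 28 |
| 24, first sentence | 90 | 28 to 118 | 0 to 28 |
| 25 | 28 | 28 to 56 | 0 to 28 |
| 26 | 28 | 28 to 56 | 0 to 28 |

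At g = 0 nothing is uncovered. With a 28-day gap, criterion 25 excludes someone who donated the day before Screening (29 days before dosing) but not someone who made an unplanned donation 7 days before dosing.

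**Step 2: which exposures fall through.**

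- Blood products, immunoglobulins and donations: any unplanned event in the gap.
- Systemic immunosuppressants: an isolated course must exceed 14 days to count at all, so it must last 15 to 28 days and be finished by Day 1. A course of 14 days or less would not meet the look-back under either anchor. A course still needed on Day 1 is caught by the anticipation clause. If days accumulate, a shorter gap course could matter: 10 days before Screening plus 5 in the gap gives 15, above 14. Criterion 18 does not say whether days accumulate.
- Other interventional studies: the same gap exists, but joining a trial is rarely unplanned.
- Long-acting biologics and intra-articular or epidural steroids: caught, because their clauses reach Day 1 or dosing.

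**Step 3: how many participants.** The documents give no event rate. Assume that 5% to 10% of participants per year have one of these events, unplanned and not otherwise excluded. Expected number = 270 × (g / 365) × annual rate.

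| Average gap | 5% per year | 10% per year |
|---|---|---|
| 7 days | 270 × 7/365 × 0.05 = 0.26 | 0.52 |
| 14 days | 0.52 | 1.04 |
| 28 days | 1.04 | 2.07 |

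For one 30-person arm, the range is 30 × 7/365 × 0.05 = 0.03 to 30 × 28/365 × 0.10 = 0.23. If one such participant did fall in a 30-person arm, that would be 1/30 = 3.3% of it.

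**The case against.** The strongest reply is that other provisions already cover most of the gap.

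- **Investigator judgment.** Criteria 8 and 10 let the Investigator exclude for conditions that may affect safety, immune response or interpretation, and criterion 9 allows exclusion because of immunosuppressive therapy. They can be applied on Day 1. In a healthy adult, a transfusion or a long steroid course will often point to such a condition. This stands in part: these criteria concern conditions and illnesses, not a donation or transfusion as such, and they are discretionary.
- **Recording and the per-protocol set.** Section 6.9.1 records immunosuppressants, immunoglobulins and blood products from Screening, and Section 6.9.2 says their use may affect per-protocol evaluability. This limits the effect on HAI results but does not prevent dosing. Section 6.9.2 does not define the study period, and donation is on neither list. SAP Section 6.4.3 defines intercurrent events as occurring after treatment starts. SAP Section 6.2.6 removes important deviations that affect immune response, but an exposure that breaches no criterion is not clearly a deviation.
- **Meaning of the forward clauses.** Participation is counted from Screening, so the clauses on plans during the study can be read as reaching into the gap. They still cover plans only. For criteria 25 and 26, which concern largely elective acts, this makes the uncovered case narrow.
- **Blood-draw safety.** The documents give no draw volume, and Section 8 caps total collection at local limits. Size cannot be judged from the documents.

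A reader might also infer that all of criteria 18 and 24 count back from Screening only. They do not: the injection sentence of criterion 18 and the biologics sentence of criterion 24 reach dosing or Day 1. Nor does the bar on waivers in Section 5 oblige a site to dose such a participant. It prevents approved departures from the criteria and leaves criteria 8 to 10 available.

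**Conclusion.** The gap is real but narrow. It is clearest for criterion 24's first sentence and for criterion 25. It is minor for criterion 18, where a new course must be long and already finished, and for criterion 26, which matters mainly for consistent wording.

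On the assumed rate of 5% to 10% per year and average gaps of 7 to 28 days, about 0.3 to 2 of 270 participants would be affected. That rate has no source in the documents and pools unlike events, so it shows scale only. The number is zero for anyone screened and dosed on the same day.

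A reader might infer that the immunogenicity results are compromised. The documents do not support that: HAI is a secondary endpoint, no hypothesis is tested, most gap exposures are recorded, and no sample size or analysis figure depends on this point. It is a cheap improvement to a stated eligibility rule.

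**What to change.** Reconcile the anchors in Section 5.2. In criterion 18 (main clause), criterion 24 (first sentence), criterion 25 and criterion 26, keep each look-back length and state that the period starts where it does now and runs through Day 1. Leave criterion 18's injection sentence and criterion 24's second sentence as they are. Apply the revised wording at the Day 1 eligibility review already in the Schedule of Activities.

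No visit, sample or assessment is added. The cost is a wording amendment, which needs ethics approval under Section 10.1.1, and very few extra screen failures: on the assumed rate, roughly the same 0.3 to 2 people.
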